5.2 Method and Timing

- Days from the assigned treatment to fistula closure: daily fistula output is assessed and recorded after fistulography with or without occlusion. Drains are removed when the drain output is ≤ 10 mL during 48 hours.
- 30-day fistula closure rate: the day on which POPF is diagnosed is day 1. The outcome is assessed at 3 months after initial removal of the drain. If recurrence is noted within 3 months after initial removal of the drain, the fistula is considered not healed by 30 days regardless of whether the drain could be removed by day 30 after the onset of POPF.
- The proportion of patients with persistent or recurrent POPF: a contrast-enhanced abdominal CT (non-enhanced CT is acceptable if contrast injection is contraindicated) is performed 3 months after removal of drains, or when there is suspicion of POPF recurrence, as suggested by the appearance of fever, ileus, or abdominal pain. Any intraabdominal fluid collection larger than 4 cm in its largest dimension is considered as evidence of POPF recurrence.
- Length of hospital stay and hospital costs after the assigned treatment: assessed at the date of discharge.
- The proportion of patients with fistula-related complications (fever/infection, ileus, bleeding/ postpancreatectomy hemorrhage (PPH) that develop after receiving the assigned treatment till 3 months after removal of drains. Patients are assessed daily for these complications during admission, and at week 1, 2, 4, 8, 12 after discharge at scheduled in-office visits.

6 Assessment of Safety

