Gradual withdrawal (2 cm every several days) of surgically placed drains in patients who are clinically stable and tolerate a diet is generally adopted to hasten closure of POPF.⁸ In brief, drain withdrawal is initiated after postoperative days 5 to 7 and continued at outpatient visits until output is less than 10 mL per day, and then the drain is removed. For high-output fistulas (> 150–200 mL of amylase-rich fluid per day), patients are initially managed with fasting and enteral or parenteral nutrition. If fistula output decreases substantially with these measures and the patient remains clinically well, drain withdrawal is initiated and oral intake is slowly restarted. If fistula output fails to decrease with these measures, drains are initially left in place to control the fistula. If the patient remains well despite high fistula output, drains are slowly withdrawn in an attempt to decrease the output

and close the fistula. If patient develops fever, abdominal pain, or an inability to tolerate oral intake, drains are not withdrawn and an abdominal computed tomographic (CT) scan is arranged. If any drainable fluid collection is identified, the patient is treated with broad-spectrum antibiotics and undergoes interventional radiology–guided drainage, which is kept in place and flushed daily. When the output decrease to less than 10 mL per day, the drains are removed.

However, the current standard practice of gradual drain withdrawal is time consuming. Although clinically stable can be discharged with the drain, the drainage tube often remains in place for a prolonged period, with patient discomfort and increased medical cost. In our pilot study, 32.5% (37/114) of POPF patients required drainage for longer than 21 days. Besides, there is also considerable risk of recurrent fluid collection along the drain tube tract after drain removal.¹¹ Measures that can accelerate drain removal and reduce the risk of recurrence may reduce POPF-related morbidity and reduce hospital costs and length of stay.

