3.1 Primary Study Endpoints/Secondary Endpoints

Efficacy end points:

- The primary efficacy end point is the days from the randomly allocated treatment to fistula closure. The date of fistula closure is defined as the date on which the drain is removed after an output of ≤ 10 mL during 48 hours, without recurrence of POPF within the next 3 months.
- Secondary efficacy end points:
 - 30-day fistula closure rate: the proportion of patients in whom the drain can be removed by 30 days after occurrence of POPF, without recurrence of POPF within the next 3 months.
 - Rate of persistent or recurrent POPF after initial drain removal: the proportion of patients with fluid collection^a on follow-up CT, which is to be performed at 3 months after removal of drain or when recurrence of POPF is suspected clinically.
 - Length of hospital stay and hospital costs after the assigned treatment.
 - Rate of fistula-related complications: the proportion of patients who develop fever/infection^b, ileus^c, postpancreatectomy hemorrhage (PPH)^d from undergoing the assigned treatment to end of follow-up.

Safety end points:

- Fever/infection* or pain** that develops within 48 hours after the allocated treatment, or any adverse events judged to be related to the treatment.

[figure not shown]
*Fever/infection: body temperature $\geq 38.5^{\circ}\text{C}$, leukocytosis (WBC count $>12,000$ /uL) or leukopenia (WBC count $<4,000$ /uL)

**Pain: new-onset or worsening of pre-existing pain (≥ 1 point increase in VAS).

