3.6 Duration

If drain(s) cannot be removed after 21 days from the occurrence of POPF, the patient is enrolled and randomized if he or she fulfils the eligibility criteria, and then receives the assigned treatment. After undergoing the assigned treatment, patients are assessed daily for drain output and any complications. Drains are removed when the drainage amount is below 10 ml during 48 hours, and patients are discharged if they tolerate oral intake well and remain afebrile for 2 days after removal of all drains. After discharge, in-office visits were scheduled at week 1, 2, 4, 8, and 12. A follow-up CT is performed when there is clinical suspicion of POPF recurrence, or at 3 months after removal of the drain, whichever comes first. Therefore, the expected duration of subject participation is between 3 to 4 months.

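### Hospital stay and cost are read at discharge, so readmissions up to 3 months do not enter them, and whether the procedure is costed is not stated

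*Combined protocol and SAP*

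**What the plan says.** Section 3.1 lists "Length of hospital stay and hospital costs after the assigned treatment" as a secondary efficacy endpoint, and section 5.1 repeats it. Section 5.2 gives the only measurement time: "Length of hospital stay and hospital costs after the assigned treatment: assessed at the date of discharge".

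Section 3.6 says when discharge occurs: "patients are discharged if they tolerate oral intake well and remain afebrile for 2 days after removal of all drains". Follow-up comes afterwards: "After discharge, in-office visits were scheduled at week 1, 2, 4, 8, and 12". On imaging, the same section states: "A follow-up CT is performed when there is clinical suspicion of POPF recurrence, or at 3 months after removal of the drain".

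The neighbouring endpoints in section 5.2 look further ahead. Fistula-related complications are those that "develop after receiving the assigned treatment till 3 months after removal of drains". The 30-day closure rate is revised to not healed "If recurrence is noted within 3 months after initial removal of the drain", and the primary endpoint also requires 3 months without recurrence (sections 3.1 and 5.1).

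The Background (section 1) argues that faster drain removal and fewer recurrences may "reduce hospital costs and length of stay".

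No section adds readmission days or costs to the stay and cost endpoints, and none says whether the assigned procedure is included in cost.

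**The concern.** There are two gaps, one at each end of the counting window.

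**End of the window.** A patient whose drain comes out early, who goes home, and who is then readmitted with a recurrence fails the closure endpoints but is still recorded as a short, cheap stay. The Background expects savings partly from fewer recurrences. An endpoint that closes at discharge cannot show most of that part, whether occlusion prevents recurrences or causes them.

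**Start of the window.** Costs counted after the assigned treatment may or may not include the treatment. Under section 3.5 both arms have fistulography, and the occlusion arm also has the catheter, guidewire, glue and drain reinsertion. If the procedure is left out, those extra items disappear from one arm only.

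At stake is whether the trial can answer the economic question in its own rationale.

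**Working it through.** The plan attaches no figure to stay or cost, so there is none to reproduce. The sample size in section 7.2 rests on a hazard ratio for drain removal and does not use these endpoints.

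**1. The windows side by side**

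| Endpoint | Counting ends |
|---|---|
| Primary (days to closure) | drain removal, conditional on no recurrence for 3 months |
| 30-day closure rate | day 30, conditional on no recurrence for 3 months after removal |
| Persistent or recurrent fistula | CT at 3 months after removal, or earlier on suspicion |
| Fistula-related complications | 3 months after removal |
| Stay and cost | date of discharge |

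For a patient discharged at the earliest permitted time, about 2 of roughly 90 days of recurrence follow-up fall inside the stay and cost window.

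**2. Days omitted within one arm**

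Omitted mean days per patient = r × L, where r is the readmission risk and L the mean length of a readmission. The documents give neither, so both are assumptions.

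| r | L = 5 | L = 7 | L = 14 |
|---|---|---|---|
| 5% | 0.25 | 0.35 | 0.7 |
| 10% | 0.5 | 0.7 | 1.4 |
| 20% | 1.0 | 1.4 | 2.8 |
| 30% | 1.5 | 2.1 | 4.2 |

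**3. Error in the comparison**

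With the same L in both arms, the error in the difference in mean stay is (r in occlusion − r in standard care) × L.

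- Equal risks: 0 × L = 0 days.
- 10-point difference: 0.10 × 5 = 0.5 to 0.10 × 14 = 1.4 days.
- 20-point difference: 0.20 × 5 = 1.0 to 0.20 × 14 = 2.8 days.

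The arm with more readmissions looks better than it is. These figures concern means; a Mann-Whitney test, which section 7.1 also allows, would be affected differently.

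**4. Sensitivity to single patients**

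The planned enrolment is 38 and 19 (section 7.2). One omitted 10-day readmission changes the arm mean by 10/38 = 0.26 days in the occlusion arm or 10/19 = 0.53 days in the standard-care arm.

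**5. Can recurrence after occlusion be taken as nil?**

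Section 1.2 reports no recurrence in 20 pilot patients. The exact two-sided 95% upper limit is 1 − 0.025^(1/20) = 0.168, or 16.8%. The pilot therefore does not rule out an appreciable risk.

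**6. Does existing follow-up reach day 90?**

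Drain removal requires 48 hours of low output, discharge requires 2 further days, and the last visit is 12 weeks (84 days) after discharge. Counting the 48 hours from treatment, with treatment on the day of randomisation, the earliest last visit is about day 2 + 2 + 84 = 88. A CT at 3 months (about 90 days) after removal falls at about day 2 + 90 = 92 or later. Day 90 is therefore within or very close to the scheduled follow-up for patients whose drain is removed.

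**The case against.** Stay from treatment to discharge is a definable outcome in its own right, and this is one of several secondary endpoints. A reader might infer that readmissions go unrecorded altogether. The documents do not support that: a hospital admission other than the index one meets the serious adverse event definition (section 6.4) and is documented in the eCRF (section 6.3), while recurrence and complications are endpoints themselves. A short index stay followed by recurrence would be visible in the report. What is missing is its conversion into days and money. Recurrence is also not the same as readmission, since a collection may first be seen on the scheduled CT.

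A reader might also infer that the rule flatters occlusion. That does not follow. The Background describes a considerable recurrence risk after ordinary drain removal, and the pilot saw none after occlusion. On that premise, leaving out readmissions would work against occlusion.

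Nor do the documents establish that procedure cost is excluded. The wording may simply mean from treatment onward, and fistulography is common to both arms. This half is an ambiguity to resolve.

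These points limit the scope and strength of the concern. They do not supply a rule that brings readmission days or costs into the two endpoints.

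**Conclusion.** The point holds for the two secondary endpoints of stay and cost. As written they close at discharge, most naturally the index discharge, and omit readmission days and costs that arise during follow-up the trial already conducts. The bias in the comparison depends on how much readmission differs between arms: none if the burden is equal, and 0.5 to 1.4 days in mean stay under the assumed 10-point difference and 5- to 14-day readmissions. Its direction is unknown. No baseline stay is given, so these days cannot be expressed as a share of the expected stay.

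The treatment of procedure cost is unclear. If it is left out, the omission of occlusion-only items favours occlusion; the amount cannot be given because the documents contain no costs.

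This should be corrected, but it does not touch the primary endpoint, the sample size or the safety endpoints.

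**What to change.** In sections 3.1, 5.1 and 5.2, define the endpoints as total inpatient days and total hospital costs from randomisation to one fixed day, the same for every patient and within existing follow-up, for example day 90. State that costs include the assigned procedure and that both endpoints include all readmissions and any re-drainage. Keep the index stay as a descriptive component.

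Starting at randomisation also gives a defined origin to patients who withdraw before receiving the assigned treatment, whom section 4.3 keeps in the analysis.

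Do not end the window 3 months after drain removal. Its length would then depend on time to removal, which the treatment is meant to change, and it would be undefined for a patient whose drain is never removed.

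The cost is a short text change in three sections, retrieval of readmission billing across centres, and a question about stays at other hospitals at visits already scheduled. Stays elsewhere would rest partly on patient report, and their costs may be harder to obtain than their days. No change to patient care is needed.

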4.6 Monitoring for treatment effect

After receiving the assigned treatment, patients are assessed daily for fistula output and fistula- or treatment-related complications until the drain is removed. After drain removal, patients are assessed according to usual postsurgical inpatient care.

5 Assessment of Efficacy

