5.1 Efficacy Parameters

- The primary efficacy end point is the days from the randomly allocated treatment to fistula closure. The date of fistula closure is defined as the date on which the drain is removed after an output of ≤ 10 mL during 48 hours, without recurrence of POPF within

the next 3 months.

- Secondary efficacy end points:
 - 30-day fistula closure rate: the proportion of patients in whom the drain can be removed by at day 30 after occurrence of POPF, without recurrence of POPF within the 3 months after removal of drain.
 - The rate of persistent or recurrent POPF after initial drain removal: fluid collection^a on follow-up CT, performed when recurrence of POPF is suspected clinically or at 3 months after removal of drain).
 - Length of hospital stay and hospital costs after the assigned treatment.
 - The rate of fistula-related complications: fever/infection^b, ileus^c, postpancreatectomy hemorrhage (PPH)^d after receiving the assigned treatment.

(a) Fluid collection: fluid accumulation on abdominal computed tomography with a diameter ≥ 4 cm.

(b) Fever/infection: body temperature $\geq 38.5^{\circ}\text{C}$, leukocytosis (WBC count $>12,000$ /uL) or leukopenia (WBC count $<4,000$ /uL). Fever/infection that is attributed to causes other than POPF is not considered as a fistula-related complication.

(c) Ileus: intolerance of oral or enteral feeding with distention of bowel on abdominal X-ray.

(d) Postpancreatectomy hemorrhage (PPH): all postoperative episodes of intraabdominal (blood in drainage fluid or hematoma on CT with dropped hemoglobin level) or gastrointestinal hemorrhage (blood in nasogastric tube, hematemesis, bloody or tarry stool), according to the International Study Group of Pancreatic Surgery (ISGPS) definition.³

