6.2 Method and Timing

Patients are assessed for vital signs and pain scores every 8 hour after the assigned treatment as per admission routine. Leukocyte count is checked at 48 hours after the assigned treatment, or earlier if fever occurs. Whether the patients develop safety end points are assessed at 48 hours after the treatment and recorded.

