6.3 Adverse Event Reporting

Any adverse event (AE) that occurs in randomized patients during the entire trial period should be carefully documented in the electronic case report form (eCRF) regardless of classification, seriousness, intensity, outcome, or causality.

Details of serious adverse events will be communicated by the local investigator to the local institutional review board (IRB).

The investigator should specify and report in the eCRF the nature of the sign or symptom, the date of onset, the date of resolution (duration), the intensity, the causality, interventions performed (if any), the relationship to trial treatment, and the outcome.

In the case of knowledge of an SAE, the investigator must immediately (within one working day of being notified of the event):

- Fill out at a minimum the following items of the internet-based SAE report: date of the AE, term of the AE, patient identification, name of reporter, treatment, result/outcome, assessment of both the seriousness and the relationship to the investigational treatment
- As soon as further information regarding the event is available (e.g. discharge note), the investigator should complete in the documentation in the eCRF and sign it electronically.
- Copies of the discharge note, of all the reports regarding examinations carried out and/or diagnostic findings should be sent to the lead investigator.

Periodic safety reports will be prepared by the lead investigator and forwarded to the IRBs of the participating sites.

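### Complications are checked daily in hospital but at five visits after discharge, and a lone white-cell value can count as infection, which can favour the arm discharged sooner

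*Combined protocol and SAP*

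**What the plan says.** Section 5.2 sets the schedule for fistula-related complications (fever/infection, ileus, haemorrhage): "Patients are assessed daily for these complications during admission, and at week 1, 2, 4, 8, 12 after discharge at scheduled in-office visits". Events count if they are ones "that develop after receiving the assigned treatment till 3 months after removal of drains".

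Section 3.6 ties discharge to drain removal: "patients are discharged if they tolerate oral intake well and remain afebrile for 2 days after removal of all drains". Section 7.2 powers the trial on a hazard ratio of 2.5 for drain removal, and length of stay is itself a secondary end point (5.1).

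Section 5.1(b) defines fever/infection as a temperature of at least 38.5 °C, "leukocytosis (WBC count $>12,000$ /uL) or leukopenia (WBC count $<4,000$ /uL"). One limit follows: "Fever/infection that is attributed to causes other than POPF is not considered as a fistula-related complication".

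On blood tests, 6.2 says: "Leukocyte count is checked at 48 hours after the assigned treatment, or earlier if fever occurs". It also has vital signs taken every 8 hours as part of admission routine. No later count is scheduled, and neither a temperature nor a count is specified for the office visits. Once the drain is out, "After drain removal, patients are assessed according to usual postsurgical inpatient care" (4.6).

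Section 7.1 lists chi-square, Fisher, t and Mann-Whitney tests and regression models for the secondary end points. It states no adjustment for time under observation.

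**The concern.** If occlusion works as hoped, it shortens drainage and so shortens the stay. The same patients then leave daily observation earlier and move to five visits over 12 weeks. With identical true risk in both arms, episodes would be more likely to be recorded in the arm that stays in hospital.

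The WBC component is the most exposed, because an event of that kind exists only if someone takes blood. The list in 5.1(b) is joined by *or*, so a single abnormal value qualifies without symptoms. Section 4.2 uses the same thresholds with *and/or*, which fits the any-one-suffices reading. After 48 hours, the number of counts a patient has is a matter of routine care and clinician choice. That these are more frequent in hospital is a reasonable inference, but the documents do not state it.

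At stake is the secondary finding on complications. Part of an apparent reduction with occlusion could reflect less looking. The primary end point and the 48-hour safety end point are not affected by this mechanism.

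**Working it through.** **The plan's own figure.** The documents give no expected rate for the complication end point, so there is none to reproduce. The arm sizes come from 7.2: 51/0.9 = 56.7, rounded to 57, split 38 and 19.

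**Inputs from the documents.** Hazard ratio 2.5; discharge 2 days after drain removal, taken as the minimum in 3.6; visits at days 7, 14, 28, 56 and 84 after discharge; daily checks in hospital.

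**Assumptions, not in the documents.** Exponential time to drain removal, capped at 90 days, with a control median of 10, 20 or 30 days. The same daily risk of a clinical episode in both arms, set so that 30% have one in 90 days: λ = −ln(0.70)/90 = 0.00396 per day. Episodes last 3 days. Every in-hospital episode is seen. After discharge an episode is seen if it is active on a visit day, and otherwise with probability s (recovered by history, a call, readmission or adverse event reporting).

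**Formula.** Recorded rate ≈ 1 − exp(−λ × E), where E is the number of days in the window on which a starting episode would be seen: in-hospital days, plus days covered by visits, plus s times the rest.

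**Worked case: control median 10 days, s = 0, common 90-day window.**
- Standard care: mean removal 14.4 days, discharge at 16.4. Visits cover about 12.6 further days (less than 5 × 3 = 15, because the last visit often falls beyond day 90). E ≈ 28.9, so the rate is 1 − exp(−0.1145) = 10.8%.
- Occlusion: mean removal 5.8 days, discharge at 7.8. Visits cover about 13.8 days. E ≈ 21.6, so the rate is 1 − exp(−0.0856) = 8.2%.

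Simulation with 200,000 patients per arm agrees to within simulation error. The table gives standard care vs occlusion, with the difference in points taken from unrounded rates:

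| Control median | s = 0 | s = 0.5 | s = 1 |
|---|---|---|---|
| 10 days | 10.8% vs 8.1% (2.6) | 21.0% vs 19.8% (1.2) | none |
| 20 days | 14.5% vs 9.9% (4.6) | 22.7% vs 20.5% (2.2) | none |
| 30 days | 17.3% vs 11.4% (6.0) | 24.0% vs 21.3% (2.7) | none |

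At s = 0, 1-day episodes give 3.0, 5.2 and 6.4 points, and 7-day episodes give 1.6, 3.4 and 4.1.

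**What one trial of 19 vs 38 would show.** With s = 0, 3-day episodes and the counting window as written, standard care has the higher observed rate in about 55%, 65% and 68% of trials. Fisher's test rejects in about 5%, 8% and 8%. These figures include the effect of the longer window in the slower arm, so they are not due to surveillance alone. With equal detection and a common window (30% in each arm) the corresponding figures are 45% and 3.7%.

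**A separate effect.** Because counting runs to 3 months after drain removal, the slower arm is also at risk for longer. With perfect detection (s = 1) that alone gives about 2.3, 3.8 and 4.9 points.

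**WBC-only events** are not in this model. Their number depends on how many unscheduled counts are taken and how often these are abnormal without infection. The documents give neither.

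**The case against.** The strongest reply is that symptomatic events are not easily lost. Fever of 38.5 °C, ileus and haemorrhage tend to bring a patient back. Visits can take a history, 5.2 triggers CT when fever, ileus or pain appears, and 6.3 says: "Any adverse event (AE) that occurs in randomized patients during the entire trial period should be carefully documented". If all of this worked fully, the surveillance gap for clinical episodes would be zero, as the s = 1 column shows. This stands, and it is why the result is a range that starts at nothing.

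The attribution rule in 5.1(b) also removes some isolated WBC values. It helps only in part: the plan gives no criteria for attribution and names no one to decide it, and an unexplained value in a patient whose drain is still in has no obvious other cause. Blinding helps that judgement but does not equalise how often blood is taken.

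Three stronger readings are tempting, and the documents do not support them.
- *The slower arm will show more events.* With 19 and 38 patients the direction is not assured.
- *WBC-only events add 6 to 19 points in controls.* This takes 3 to 4 extra counts at a 2% to 5% false abnormal rate: 1 − 0.98³ = 5.9% and 1 − 0.95⁴ = 18.5%. No extra counts are scheduled, and both rates are assumed. Repeat counts in one patient are treated as independent, and the attribution rule is given no weight.
- *A 2-day fever at home is caught only 12% of the time, and a 5-day fever 30%.* The arithmetic is right for visit-day overlap (10/84 and 25/84 start days), but it ignores history-taking and adverse event reporting.

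**Conclusion.** The concern holds in limited form. Intensity of observation depends on length of stay, stay depends on drain removal, and the listed tests do not allow for it. The expected direction favours the arm discharged sooner, which is occlusion if it works. For clinical episodes the size is about 0 to 3 points at a control median of 10 days and up to about 6 points at 30 days. That range rests on equal daily risk, 3-day episodes, a 30% background rate and a common 90-day window, and its position within the range depends on how many between-visit episodes are recovered. The WBC-only contribution cannot be sized from the documents. This bears on one secondary end point and merits a cheap wording change.

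**What to change.** In 5.1(b), for the main analysis of fistula-related complications, state that a WBC value outside 4,000 to 12,000 /uL is not an event on its own. It counts only with fever at the stated threshold or other clinical evidence of infection, and the plan should list what that evidence is. An alternative is to count WBC-only events only from the 48-hour sample, which is scheduled alike in both arms. That option would largely repeat the safety end point in 6.1, so the first is cleaner. Keep the present definition as a supportive analysis, and leave 6.1 unchanged.

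Do not add a condition that the event led to treatment or imaging. Ileus in 5.1(c) already needs an X-ray, and in the pathway described in 1.5 fever brings antibiotics and CT. Such a condition would itself depend on being in hospital.

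Cost: definition wording only, with no new visits or tests, and slightly fewer events in the main count. The change takes out the component most dependent on testing frequency. It does not equalise detection of clinical episodes, and it does not address the counting window that runs to 3 months after drain removal, which needs its own correction.
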